5. STUDY POPULATION

Prospective approval of protocol deviations to recruitment and enrollment criteria, also known as protocol waivers or exemptions, is not permitted. Participants are eligible to be included in the study only if all of the following criteria apply:

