5.1. Inclusion Criteria

AGE
1. At least 18 to 75 years of age at the time of signing the informed consent [if country/site age requirements for consent differ, the more stringent (e.g., higher age) restriction will be required for that country/site].
TYPE OF PARTICIPANT AND DISEASE CHARACTERISTICS
2. Participants who are eligible to be treated with PegIFN (Table 8)
3. Documented chronic HBV infection ≥ 6 months prior to screening AND currently receiving stable NA therapy except telbivudine, defined as no changes to their NA regimen from at least 6 months prior to screening and with no planned changes to the stable regimen over the duration of the study
4. Plasma or serum HBsAg concentration > 100 IU/mL
5. Plasma or serum HBV DNA < 90 IU/mL
6. Alanine Transaminase (ALT) ≤ 2 X ULN

SEX
7. Male and/or Female 
 a. A male participant is eligible to participate if they agree to the following during the intervention period and for at least 90 days after the last dose of study treatment 
 i. Refrain from donating sperm ii. AND be abstinent from heterosexual intercourse as their preferred and usual lifestyle (abstinent on a long term and persistent basis) and agree to remain abstinent OR Must agree to use contraception/barrier as detailed below 
 1. Agree to use a male condom [and should also be advised of the benefit for a female partner to use a highly effective method of contraception as a condom may break or leak] when having sexual intercourse with a woman of childbearing potential who is not currently pregnant b. A female participant is eligible to participate:

- i. If she is not pregnant or breastfeeding
 - ii. AND at least one of the following conditions applies:
 1. Is not a woman of childbearing potential (WOCBP) as defined in Section 10.4 Contraception and Barrier Guidance
 2. Is a WOCBP and using a contraceptive method that is highly effective (with a failure rate of <1% per year), preferably with low user dependency during the intervention period and for at least 90 days after the last dose of study treatment
- A WOCBP must have a negative highly sensitive pregnancy test (urine or serum as required by local regulations) within 24 hours before the first dose of study intervention, see Section 10.2.

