4.1.1. General Methodology

Participants who prematurely withdrew from study will not be replaced.

In the case of incorrect randomization stratification assignment at the time of randomization, the analyses will be performed based on the actual stratum per data collected in the baseline lab electronic Case Report Form (eCRF). In the case of randomization to the incorrect strata (i.e., if a HBsAg subject is randomised to the HBeAg strata, or vice versa), analysis will be performed based on the actual strata the subject should have been assigned to.

Unless otherwise specified, continuous data will be summarized using descriptive statistics: n, mean, standard deviation (std), median, minimum, and maximum. Categorical data will be summarized as the number and percentage of participants in each category.

Unless otherwise specified, CIs will use 95% confidence levels.

HBV DNA, HBsAg and HBeAg levels below the LLOQ will be imputed for summaries of actual values and change from baseline. The numeric values for HBV DNA <LLOQ (LLOQ=20 IU/mL) will be imputed as 19.9. The numeric values for HBsAg <LLOQ (LLOQ=0.05 IU/mL) will be imputed as 0.04. The numeric values for HBeAg <LLOQ (LLOQ=0.06 U/mL) will be imputed as 0.05.”

HBV DNA (IU/mL) and HBV RNA (copies/mL) levels that are “TND” will be imputed as 1. HBcrAg (Log₁₀ U/mL) values that are “TND” will be imputed as 0. Values <LLOQ are imputed based on the number of significant digits, similar to other lab parameters.

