- Categorical changes from baseline in HBsAg (e.g., <0.5, ≥0.5, ≥1, ≥1.5, ≥3 log₁₀ IU/mL) and in HBV DNA (e.g., <1, ≥1, ≥2, ≥3 log₁₀ IU/mL). Change from baseline will be presented at each visit and for the following time periods: up to and including Week 6, up to and including Week 12, up to and including Week 24, up to and including off-treatment Week 24. Data will be presented overall and by the baseline stratification factors defined in [Table 1](#). Data will be summarized using planned visits.
- ALT normalisation (ALT ≤ ULN) over time in absence of rescue medication in participants with baseline ALT > ULN.
- HBe antibody (anti-HBeAg) levels.

Population Summary: Percentage of participants in each category for each treatment arm.

Continuous Variables

Continuous variables for the secondary objective are defined as follows:

- Actual values and change from baseline over time of HBsAg, HBV DNA, and HBeAg levels (only in HBeAg Positive Participants at baseline).
- Actual values and change from baseline over time for HBs antibody (anti- HBsAg) levels.
- Actual values and change from baseline over time for ALT.

Population Summary: Mean values and mean changes from baseline of each variable for participants in each treatment arm.

Time to Event Variables:

A time to event variable for this objective is defined as:

- Time to ALT normalisation in absence of rescue medication in participants with baseline ALT>ULN.

Population Summary: Turnbull's estimator for nonparametric estimation of Time to ALT normalisation in each treatment arm.

ALT normalization is defined in participants with ALT>ULN at baseline as a return to <ULN (ULN = 40 for males and 33 in females). Time to ALT normalization is defined as time from baseline to the first follow-up where subject's ALT has returned to normal.

For participants who withdraw from the study or Participants with ALT>ULN at the end of study (EoS), time to ALT normalization will be censored after the time of the last visit with non-missing ALT value available. Participants who receive rescue medication cannot go on to achieve the event of 'ALT normalization in the absence of rescue medication'; such participants will be censored at the end of the follow up period.

In order to determine if the addition of a PegIFN treatment after completing 12 or 24-weeks of Bepirovirsen delays relapse, an additional time to event variable is defined as follows:

- Time from Bepi EOT to Relapse by HBsAg Categories

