Phase of HBV Infection (Strict Criteria)	
Phase 1; Phase 2; Other HBeAg-positive; Phase 3; Phase 4; Other HBeAg-negative, where phases are defined as below.
 
Phase 1 = HBeAg-positive, ALT ≤ ULN during screening and at baseline, HBV DNA > 10⁶ IU/ml during screening and at baseline Phase 2 = HBeAg-positive, ALT > ULN either during screening or at baseline, HBV DNA > 10⁴ IU/ml during screening and at baseline Other HBeAg-positive = HBeAg-positive, neither Phase 1 nor Phase 2 Phase 3 = HBeAg-negative, ALT ≤ ULN during screening and at baseline, HBV DNA < 20,000 IU/ml during screening and at baseline Phase 4 = HBeAg-negative, ALT > ULN either during screening or at baseline, HBV DNA > 2,000 IU/ml during screening and at baseline Other HBeAg-negative = HBeAg-negative, neither Phase 3 nor Phase 4

Phase of HBV Infection (Loose Criteria)	
Phase 1 loose; Phase 2 loose; Phase 3 loose; Phase 4 loose, where phases are defined as below.
 
Phase 1 loose= HBeAg-positive, ALT ≤ ULN during screening and at baseline Phase 2 loose = HBeAg-positive, ALT > ULN either during screening or at baseline Phase 3 loose = HBeAg-negative, ALT ≤ ULN during screening and at baseline Phase 4 loose = HBeAg-negative, ALT > ULN either during screening or at baseline

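### With entry HBV DNA below 90 IU/mL, declines of ≥2 and ≥3 log10 cannot be reached from an eligible baseline, a ≥1 log10 decline depends on TND being imputed as 1, and three strict HBV-phase subgroups are empty

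*SAP*

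**What the plan says.** **Entry.** Protocol 5.1 requires "Plasma or serum HBV DNA < 90 IU/mL" on background nucleos(t)ide (NA) therapy, "defined as no changes to their NA regimen from at least 6 months prior to screening". Protocol 5 adds that prospective approval of deviations from the entry criteria, "also known as protocol waivers or exemptions, is not permitted".

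**Imputation.** SAP 4.1.1 states: "The numeric values for HBV DNA <LLOQ (LLOQ=20 IU/mL) will be imputed as 19.9". It also states: "HBV DNA (IU/mL) and HBV RNA (copies/mL) levels that are “TND” will be imputed as 1". Baseline (SAP 4.1.2) is the latest non-missing pre-dose value, so it need not equal the screening value.

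**HBV DNA outputs.** SAP 4.3.1.1 plans categorical change from baseline in HBsAg "and in HBV DNA (e.g., <1, ≥1, ≥2, ≥3" log10 IU/mL), by visit and for cumulative periods to Weeks 6, 12 and 24 and to off-treatment Week 24. Interim item 4 in SAP 4.7.2 repeats the cut-offs, without the e.g., as declines. Item 5 there summarises actual values and change in log10 HBV DNA. Both items are also end-of-study outputs according to SAP 4.7.2. Protocol 3 and 9.4.3.1 list categorical change for HBsAg only, but they do list mean HBV DNA change as a secondary variable.

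**Phase subgroups.** SAP Table 7 defines strict phases partly by viral load. Phase 1 needs more than 10^6 IU/mL and Phase 2 more than 10^4 IU/mL. Phase 4 needs "HBV DNA > 2,000 IU/ml during screening and at baseline". Each limit applies both at screening and at baseline. Strict Phase 3 needs less than 20,000 IU/mL. The loose version uses HBeAg status and ALT only.

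**The concern.** The cut-offs suit patients who start with measurable viraemia. Here everyone is already suppressed by NA therapy, so there is little HBV DNA left to lose. Two rows of the table look impossible to fill. The remaining ≥1 log10 row looks as if it is driven by the choice of 1 as the number standing in for TND.

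If so, the secondary table and the mean log10 change could show a fall of more than 1 log10 when a sample moves between two unquantifiable states. Both arms receive GSK3228836 followed by PegIFN (Protocol 4.1), so there is no NA-only arm from which to judge how much of that movement occurs anyway. If the cumulative periods count any qualifying visit, one TND result among near-weekly samples is enough.

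Table 7 appears to share the root cause: SVR rates with posterior summaries are planned by subgroups, some of which eligible participants cannot enter.

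**Working it through.** The plan gives no figure of its own on this point, so the check is direct arithmetic.

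**Inputs.** Entry ceiling 90 IU/mL (Protocol 5.1). LLOQ 20, below LLOQ = 19.9, TND = 1 (SAP 4.1.1). Cut-offs 1, 2 and 3 log10 (SAP 4.3.1.1 and 4.7.2).

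**Step 1: largest decline.** Decline = log10(baseline / later value).

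| Baseline (IU/mL) | to TND (1) | to below LLOQ (19.9) | to a quantified 20 |
|---|---|---|---|
| 19.9 (detected, below LLOQ) | 1.299 | 0.000 | −0.002 |
| 20 | 1.301 | 0.002 | 0.000 |
| 50 | 1.699 | 0.400 | 0.398 |
| 89.9 | 1.954 | 0.655 | 0.653 |

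No entry-eligible baseline reaches 2. Without TND, none reaches 1. With TND, every detected baseline reaches 1. A change between two unquantified results (19.9 to 1) therefore scores about twice a measured fall from 89.9 to below LLOQ (1.299 against 0.655). The reverse move, TND to detected below LLOQ, scores a rise of 1.299.

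**Step 2: baseline needed to meet each cut-off.**

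| Cut-off | if later value is TND | if later value is below LLOQ |
|---|---|---|
| ≥1 log10 | 10 | 199 |
| ≥2 log10 | 100 | 1,990 |
| ≥3 log10 | 1,000 | 19,900 |

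A Day 1 pre-dose value above the entry limit is the only route to ≥2 (100 or more, then TND), or to ≥1 without TND (199 or more, then below LLOQ).

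**Step 3: effect on a summary.** The documents do not say how often results switch between TND and detected below LLOQ, so this is per participant in an arm of about 50 (Protocol 9.2). Each switch from detected-below-LLOQ at baseline to TND adds 1/50 = 2 percentage points to the ≥1 row at that visit and moves the mean by 1.299/50 = 0.026 log10. As an assumed range, 1 to 10 such participants would give 2 to 20 points, and 0.026 to 0.26 log10 if no switches go the other way.

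**Step 4: contrast with HBsAg.** Entry requires HBsAg above 100 IU/mL, and below LLOQ is imputed as 0.04. log10(100/0.04) = 3.40, so the HBsAg cut-off of ≥3 is reachable. The problem is specific to HBV DNA.

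**Step 5: strict phases.** Ratio of the required screening value to the entry ceiling:
- Phase 1: 10^6/90 ≈ 11,111
- Phase 2: 10^4/90 ≈ 111
- Phase 4: 2,000/90 ≈ 22

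Because the limit applies at screening as well as at baseline, a Day 1 rise does not fill these categories. All HBeAg-positive participants fall into the strict Other group. The 20,000 limit excludes no one with an entry-eligible value, so strict Phase 3 coincides with loose Phase 3, and strict Other HBeAg-negative coincides with loose Phase 4.

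**The case against.** The strongest reply is that nothing important rests on these outputs. They are descriptive, and a TND result simply counts as below LLOQ when SVR is derived (SAP 4.2.2.1), so neither imputed value touches the primary endpoint. The interim predictive probabilities use counts of virologic responders. This stands. A reader might infer that the primary result is distorted, and the documents do not support that.

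Other replies:

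- **Wording.** SAP 4.3.1.1 speaks of changes and marks the cut-offs as examples; only SAP 4.7.2 says decline. This stands as a qualification: if rises are counted, ≥2 and ≥3 are reachable through viral rebound.
- **Absolute impossibility.** The limits hold for baselines below 90. A Day 1 rise is allowed by the baseline definition, so it would be too strong to say that no participant could ever reach ≥2.
- **Proof of harm.** A reader might conclude that the tables will report assay fluctuation as drug effect. The switching rate is not given, so the documents show that the output cannot separate the two, and no more.
- **Mean change.** It is tempting to say that mean HBV DNA change should be removed. It is a protocol-defined secondary variable, so deletion would go too far.
- **Already covered elsewhere.** TND over time (item 13) and SVR using TND (SAP 4.7.7) are planned at the interim. SAP 4.7.2 does not carry item 13 to the end of study, but the exploratory efficacy and virology text is redacted, so similar tables may exist there.
- **Empty rows.** SAP 4.6.1 allows categories with fewer than five participants to be redefined, and other Table 7 rows (for example age 85 or over) are also empty by eligibility. Empty rows alone are cosmetic. That does not help the ≥1 row or the mean change, which are not empty.

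**Conclusion.** The point holds for baselines below 90 IU/mL. The maximum decline is 1.954 log10, so the ≥2 and ≥3 decline rows cannot be filled. A decline of ≥1 log10 occurs only when TND is scored as 1, and the mean log10 change carries the same constant. The single exception is a Day 1 pre-dose value above the entry limit. Strict Phases 1, 2 and 4 contradict the entry criterion at screening and are empty. For entry-eligible values the strict scheme adds nothing to the loose one, which can be filled.

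This rests on the SAP imputation being applied as written to log10 change, and on entry criterion 5 being enforced. It is worth correcting because the ≥1 row would be read as antiviral decline in a trial with no NA-only comparator. It does not affect SVR, and the size of the effect on the tables cannot be stated from the documents.

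**What to change.** 1. In SAP 4.3.1.1 and SAP 4.7.2 item 4, replace the HBV DNA log10 categories with a by-visit shift table from baseline: TND, detected below LLOQ, at or above LLOQ. The categories are a SAP addition, so the protocol does not need to change.
2. Report the proportion with confirmed HBV DNA at or above LLOQ, in line with the second limb of the breakthrough definition in Protocol 8.7, unless the redacted text already plans it.
3. Keep the protocol-specified mean HBV DNA change. Add a footnote giving the imputed values (19.9 and 1) and stating that changes between TND and below LLOQ are not quantified.
4. In SAP Table 7, drop the strict HBV-phase subgroup and label the loose one as HBeAg status by baseline ALT on NA therapy.
5. Record these changes in SAP Table 10 (SAP 4.8), which does not currently mention the HBV DNA categories.

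The cost is wording and a small rework of table shells; no new data are needed.

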
Efficacy: To assess the efficacy of GSK3228836 and PegIFN therapy on biomarkers and virus specific antibody responses
	
The Estimand supporting the objective is defined as:
 
 • Population: Participants with CHB on stable NA therapy; For the time to alanine aminotransferase (ALT) normalisation variable, population will be aforementioned participants with baseline ALT >upper limit normal (ULN). • Treatment: 300 mg GSK3228836 for 12, or 24 weeks followed by 24 weeks of PegIFN therapy while on stable NA therapy • Categorical Variables: 
 ○ Achieving HBsAg <LLOQ and HBV DNA <LLOQ at two time points: (1) the planned end of treatment and (2) at the end of 24 weeks follow-up ○ Categorical changes from baseline in HBsAg (e.g., <0.5, ≥0.5, ≥1, ≥1.5, ≥3 log₁₀ IU/mL) at each scheduled visit or analysis window. ○ ALT normalisation (ALT ≤ULN) over time in absence of rescue medication in participants with baseline ALT >ULN Population summary is the percentage of participants in each category for each treatment group. ○ HBe antibody (anti-HBeAg) levels. • Continuous Variables: 
 ○ Actual values and change from baseline over time for HBsAg, HBV DNA and hepatitis B virus e-antigen (HBeAg) ○ Actual values and change from baseline over time for HBs antibody (anti-HBsAg) levels over time ○ Actual values and change from baseline over time for ALT Population summary is the mean values and the mean changes from baseline of each

Objectives	Estimands

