9.4.3. Secondary Endpoints

9.4.3.1. Secondary Estimands

Three groups of estimands are defined for the secondary efficacy objectives. Categorical definitions for secondary analyses will be provided in the RAP.

1. Estimands supporting secondary objective of assessing the efficacy of GSK3228836 and PegIFN sequential therapy on biomarkers and virus specific antibody responses are defined as follows:
 - Population: Participants with CHB on stable NA therapy; For the time to ALT normalisation variable, population will be aforementioned participants with baseline ALT $> \text{ULN}$.
 - Treatment: 300 mg GSK3228836 for 12 or 24 weeks followed by up to 24 weeks of PegIFN therapy while on stable NA therapy
 - Intercurrent Events: Discontinuation of, interruption in, and non-adherence to GSK3228836 and PegIFN will be ignored (treatment policy). PegIFN ineligibility will be ignored (treatment policy); Rescue medication will be ignored (treatment policy), except for ALT normalisation which can only be achieved in the absence

- of rescue medication; Wide disruptive events (such as COVID-19 pandemic) leading to discontinuation of, interruption in, and non-adherence to GSK3228836 and PegIFN will be ignored (treatment policy strategy).
- Categorical Variables:
 - Achieving HBsAg <LLOQ and HBV DNA <LLOQ at two time points: (1) the planned end of treatment and (2) at the end of 24 weeks follow-up
 - Categorical changes from baseline in HBsAg (e.g., <0.5, ≥0.5, ≥1, ≥1.5, ≥3 log₁₀ IU/mL).
 - ALT normalisation (ALT ≤ ULN) over time in absence of rescue medication in participants with baseline ALT > ULN
 - HBe antibody (anti-HBeAg) levels
 - Population summary of Categorical Variables: percentage of participants in each category for each treatment arm
 - Continuous Variables:
 - Actual values and change from baseline over time of HBsAg, HBV DNA, and HBeAg levels
 - Actual values and change from baseline over time for HBs antibody (anti-HBsAg) levels over time
 - Actual values and change from baseline over time for ALT.
 - Population summary of Continuous Variables: mean values and mean changes from baseline of each variable for participants in each treatment arm
 - Time to Event Variable:
 - Time to ALT normalisation in absence of rescue medication in participants with baseline ALT > ULN
 - Population summary of Time to Event Variable: Turnbull's estimator for non-parametric estimation of Time to ALT normalisation in each treatment arm

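### Time to ALT normalisation in the SAP requires ALT strictly below ULN, while the protocol and the SAP's own by-visit endpoint count ALT equal to ULN as normal

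*SAP*

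**What the plan says.** The protocol, in the Synopsis and again in Sections 3 and 9.4.3.1, lists as a categorical secondary variable "ALT normalisation (ALT ≤ULN) over time in absence of rescue medication in participants with baseline ALT >ULN". It then names a time-to-event variable, time to ALT normalisation, summarised by Turnbull's "estimator for non-parametric estimation of Time to ALT normalisation in each treatment arm". It gives no second threshold for that variable, so at or below ULN is its only definition of normalisation.

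SAP Section 4.3.1.1 repeats the by-visit endpoint with the same threshold: "ALT normalisation (ALT ≤ ULN) over time in absence of rescue medication in participants with baseline ALT > ULN". Further down, under the time-to-event variables, the threshold becomes strict: "ALT normalization is defined in participants with ALT>ULN at baseline as a return to <ULN (ULN = 40 for males and 33 in females"). The event time is a single visit: "Time to ALT normalization is defined as time from baseline to the first follow-up where" ALT is normal again. The summary is still Turnbull's "estimator for nonparametric estimation of Time to ALT normalisation in each treatment arm".

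On censoring, the SAP names two groups: those who withdraw, and "Participants with ALT>ULN at the end of study (EoS), time to ALT normalization will be censored after the time of the last visit" with an ALT value. Participants who take rescue medication are censored at the end of follow-up. Table 10 of the SAP, which lists departures from the protocol analyses, has no entry for a changed ALT threshold, and the version history has none either.

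**The concern.** Two secondary results share one name and use different rules at one value. A man with ALT 40 or a woman with ALT 33 is normal in the by-visit table and not normal in the time-to-event analysis. The value is not remote in this trial. Entry requires "Alanine Transaminase (ALT) ≤ 2 X ULN", so those who enter the ALT analyses with a raised value mostly start fairly near the limit and may pass through it on the way down.

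At stake is whether the two ALT displays can be reconciled participant by participant, and whether every participant in the time-to-event analysis has a defined status. The primary endpoint is not touched.

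**Working it through.** The documents give no sample size, event rate or precision for this endpoint, so there is no planned figure to reproduce. The check sets the rules side by side, then gauges size on stated assumptions.

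**1. The rules at the limit** (ULN 40 for males, 33 for females, from SAP 4.3.1.1):

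| ALT (male / female) | By-visit, ≤ULN | Time to event, <ULN | End-of-study censoring, >ULN |
|---|---|---|---|
| 39 / 32 | normal | event | no |
| 40 / 33 | normal | no event | no |
| 41 / 34 | not normal | no event | yes |

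The rules disagree only in the middle row. There, three outcomes are possible:
- ALT later falls below ULN: the event is dated at that later visit.
- ALT never falls below ULN and ends above it: the participant is censored, although normal at a visit in the other table.
- ALT never falls below ULN and ends exactly at it, in a completer without rescue medication: neither an event nor covered by the censoring rule.

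**2. Which rule is the outlier.** The population for the time-to-event variable is baseline ALT above ULN, so a man at 40 is left out as not raised; at follow-up the same 40 does not count as a return to normal. The censoring rule (above ULN) is the complement of at or below ULN, not of below ULN. The baseline ALT subgroup in SAP Table 7 splits at ≤ULN against >ULN. Everything except the one strict sign treats ULN as normal.

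**3. Size, on assumed inputs.** Assumptions: ALT in whole units; 20,000 males; personal mean ALT uniform between 0.7 and 1.6 times ULN; log-normal variation within person; visits approximating the Arm 1 schedule. The shares are:
- tie = visits with ALT = ULN, divided by all visits;
- permanent conflict = participants ever ≤ULN but never <ULN, divided by all participants;
- later date = first visit <ULN falls after first visit ≤ULN, among participants with both;
- uncovered = last ALT = ULN and never <ULN, divided by all participants.

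| Within-person log-SD | Tie | Ever ≤ULN | Ever <ULN | Permanent conflict | Later date | Uncovered |
|---|---|---|---|---|---|---|
| 0.05 | 2.8% | 47.9% | 44.8% | 3.1% | 14.5% | 0.13% |
| 0.15 | 2.8% | 78.1% | 74.2% | 3.9% | 12.1% | 0.13% |
| 0.25 | 2.6% | 97.7% | 96.6% | 1.2% | 9.7% | 0.04% |

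A second simulation assumed baseline ALT 41-80, long-run ALT of 25, 35 or 40, and within-person CV of 10-20%. It gave ties at 2-5% of visits and a different first-normal date in 14.6-32.5% of participants.

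In head count, suppose 10 to 40 participants have raised baseline ALT (an assumption). Permanent conflict then affects between 10 × 0.012 = 0.12 and 40 × 0.039 = 1.56 people.

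**4. The estimator.** Turnbull's method takes an interval for each event. If the first normal visit is entered as an exact time, it reduces to Kaplan-Meier. With 300 simulated participants, exponential times with mean 30 weeks and 10% missed visits, the single-time version matched the ordinary empirical curve within 0.002. Against true intervals it gave 52.0% v 52.2% at week 24 and 84.7% v 85.5% at week 60. The largest gap among the weeks compared was 0.8 points.

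**The case against.** The strongest reply is that this is a slip of one character in one of many descriptive secondary variables. The surrounding text already shows the intended meaning, and a sensible programmer would read it that way. The conflict over who normalises needs ALT exactly at ULN and never lower, which may affect no one or one or two people. ALT reporting precision is not stated anywhere, so whole-number ties are an assumption. All of this stands, and it limits the point to a small one. It does not remove it: the strict sign is the written rule for this variable, and a programmer who follows it departs from the protocol without a declared change.

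A reader might infer three stronger things.
- **Median time biased late by weeks.** Simulated shifts of 7 to 77 days can be produced, but the largest come from assuming that ALT settles near ULN, and the inputs are not in the documents. A stricter threshold is also a different definition rather than a bias.
- **The Turnbull wording is an error that changes who normalises.** It can affect only the dating. The SAP does not say that the first normal visit enters as an exact time; that visit is also the right end of the interval Turnbull needs. The text is incomplete, not shown to be wrong.
- **The arm comparison is distorted because visits thin out at different weeks.** The summary is per arm, and no formal test is planned.

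**Conclusion.** The inconsistency is real and can be read from the text alone. The SAP's time-to-event definition of ALT normalisation differs from the protocol, from the SAP's by-visit endpoint, and from its own population and censoring rules. It leaves a small class of completers without a defined status.

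The effect is probably small: about 2-5% of visits at the limit, 1-4% of participants in permanent conflict, and roughly 10-33% with a later event date. These figures depend on whole-unit reporting and on assumed ALT levels and variability. The tabulated simulation used the male limit, held each person's mean constant, included no flares and was not restricted to raised baseline ALT. The figures show scale and are not forecasts. The direction is certain: the strict rule can only delay or remove events. The correction should be made because it is exact and nearly free, not because a conclusion of the trial depends on it. The interval for Turnbull's estimator is a secondary clarification.

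**What to change.** In SAP 4.3.1.1, under the time-to-event variables, change the return threshold from <ULN to ≤ULN, and state that the limits of 40 (males) and 33 (females) apply to both ALT endpoints. The end-of-study censoring rule then covers exactly the completers without an event, apart from the separate rule for rescue medication.

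As a clarification, add how the event enters the estimator: the interval runs from the last ALT visit above ULN before the first visit with ALT ≤ULN, up to that first visit, in the absence of rescue medication. The qualifier about preceding the first normal visit is needed because ALT can rise again later. Right-censor participants with no ALT ≤ULN at their last non-missing ALT visit, and keep the existing rule for rescue-medication users.

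The cost is one character, a statement of the common limits, a short addition on the interval, and a minor programming change. No new data are needed.
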